2.3. Hypotheses

Primary Hypothesis

1. Approximately 15-minutes after lens insertion, the percentage of lens fits with absolute rotation less than or equal to 10 degrees will be superior to 80%.

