4.2. Study Design Rationale

A non-dispensing, single-visit, 2x2 bilateral crossover design was considered to be the optimal design to evaluate the primary objective of absolute rotation of the investigational lenses 15-minutes after insertion. The lens design of the investigational multifocal toric lenses in this study was modified after reviewing the results from a previous study [REDACTED]. Since the primary objective is to assess the absolute rotation, a limited number of lens powers were

Clinical Study Protocol

Johnson & Johnson Vision Care, Inc.

chosen to be included in this study, as rotation and lens power are expected to be independent. Lens powers in combinations of plus and minus sphere powers (-3.00, +3.00 DS), low and high cylinder powers (-1.00, -1.75 DC), and cylinder axes (90°, 180°) were chosen to approximately represent the range of possible refractive errors. A 2x2 Crossover design is more cost effective compared to a parallel study as fewer subjects are required to achieve the same pre-specified statistical power. A washout period of 15-minutes will be used between study treatments. Due to the objective nature of the primary endpoint a washout of 15-minutes is considered sufficient to minimize any effects from the previous treatment.

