14.2. Sample Size Justification

This study was designed and powered to test that the percentage of lens fit with absolute rotation for both study lenses is superior to 80% 15-minutes after insertion. The sample size

Clinical Study Protocol

Johnson & Johnson Vision Care, Inc.

was calculated using a 2-sided type I error rate of 5% with at least 80% statistical power. Historical data from [REDACTED] and [REDACTED] was both utilized in estimation of the sample size.^{7,12} Table 6 below provides details regarding each clinical study and Table 7 summarizes the absolute rotation for each study and lens for all lens fits (including any modifications).

Table 6 Summary of Historical Clinical Studies

Study ID	Design	Population	Age Range (years)	Number Enrolled	Number Dispensed	Number Completed
[REDACTED]	Single arm	Hyperopes + Myopes	40 to 70	95	86	84
[REDACTED]	2x2 crossover	Myopes	18 to 39	103	98	93

Table 7 Summary of Absolute Rotation by Lens – 15-Minutes After Insertion

	AOFA N=202	Aurora A		
		Hyperopes N=114	Myopes N=136	Total N=250
Absolute rotation n(%)				
0 to 5	174 (86.1)	85 (74.6)	96 (70.6)	181 (72.4)
>5 to 10	19 (9.4)	14 (12.3)	21 (15.4)	35 (14.0)
>10 to 15	8 (4.0)	7 (6.1)	11 (8.1)	18 (7.2)
>15	1 (0.5)	8 (7.0)	8 (5.9)	16 (6.4)
Total	202	114	136	250
Absolute rotation < 10° n(%)				
Yes	193 (95.6)	99 (86.8)	117 (86.0)	216 (86.4)
No	9 (4.5)	15 (13.2)	19 (14.0)	34 (13.6)
Total	202	114	136	250

N=Number of lens fits.

Based on the results from [REDACTED], the lens design was modified to improve the absolute rotation. The changes implemented into the lens design are more closely aligned with the Acuvue Oasys for Astigmatism lens design utilized in [REDACTED]. However, as indicated in Table 5, [REDACTED] enrolled non-presbyopic myopic subjects only. In general, presbyopic subjects have been found to more contact lens rotation compared to non-presbyopic subjects, therefore,

Clinical Study Protocol **Johnson & Johnson Vision Care, Inc.**

results from both studies were considered when choosing different scenarios of reference rates.^{7,12}

Shown in Table 6 above, [REDACTED] had rates of 86% and 96%, respectively. Therefore, different scenarios used for the sample size and power calculations were chosen within that range. Furthermore, taking into consideration that this study will enroll subjects aged 40 to 70, more conservative rates of 88%, 89% and 90% were used.^{7,12}

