Sample size estimates were carried out using Monte Carlo methods. A total of 2000 boot-strap samples were simulated using different scenarios for the reference rate for event Y and interclass correlations of 0.80 to model the covariance between the left and right eyes within the same treatment, and 0.50 to model both the covariance between treatments within the same eye as well as between eyes and treatments. Each boot-strap sample was analyzed using a generalized linear mixed model with a binary distribution and the logit and the link function. Lens was included as the only fixed effect. Errors between measurements within the same subject and period were modeled using a variance component covariance structure (VC). The Kenward and Roger Method was used for the denominator degrees of freedom.¹³ The percentage of lens fits with absolute rotation less than 10° was constructed using 95% confidence intervals for the least-square mean. Success for each boot-strap sample was declared if the lower limit of the 95% CI was above 80%. Table 8 below displays the number of subjects required to test superiority for the primary hypothesis for each study lens.

While subjects will wear the study lenses in a random order data collected during evaluations in period 2 are not expected to be influenced by the lenses worn during period 1 since a wash-out 15 -minutes will be utilized between study lenses and, subjects' absolute rotation depends on the study lens on eye at that moment of data collection.

Table 8 Statistical Power for 80 Subjects to complete by Reference Rate

	Reference Rate		
	88%	89%	90%
Statistical Power (%)	87.7	95.1	98.3

Up to 90 subjects (45 Hyperopes and 45 Myopes) will be enrolled with the target of 80 subjects (40 Hyperopes and 40 Myopes) to complete the study. Since this is a single-visit, non-dispensing study, a high rate (> 10%) of subject drop-out is not expected to occur. However, subject drop-out rate will be monitored. If an unexpectedly high dropout rate is observed, then enrollment maybe be increased to ensure the minimum number of subjects required to test the primary hypothesis complete the study.

Clinical Study Protocol

Johnson & Johnson Vision Care, Inc.

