14.5. Primary Analysis

The primary analysis will be conducted on the ITT population.

Absolute Rotation $\leq 10^\circ$

Absolute rotation data collected 15-minutes after insertion will be dichotomized as Y=1 if the absolute rotation is less than 10° and Y=0 otherwise for the purpose of analysis. Y will be analyzed using a generalized linear mixed model with a binary distribution and the logit as the link function. Sequence of lens wear, period and lens type will be included in the model as fixed effects. Other characteristics such as age may be included as covariates in the model. Site and subject will be included as random effects (G-side). The covariance measurements within the same subject (between eyes) across study periods will be modeled using an unstructured (UN) covariance structure. The Kenward and Roger method⁷ will be used for the denominator degrees of freedom. If none of the fixed effects are significant, the percentage of lens fits with absolute rotation less than 10° will be estimated by combining data from both lenses using 2-sided 95% confidence intervals.

The Model:

Let y_{ijklmn} denote the absolute rotation for the n^{th} eye from the m^{th} subject at the l^{th} site assigned to the k^{th} sequence during the j^{th} period for the i^{th} lens ($i=1,2$; $j=1,2$; $k=1, 2$; $l=1, \dots, l_m$; $n=1,2$). The likelihood will be constructed as follows:

$$\text{logit}(y_{ijklmn}) = \beta_0 + \beta_1 \text{Lens}_{i[j,k]} + \beta_2 \text{Period}_j + \beta_3 \text{Sequence}_k + \delta_l + \gamma_{l_m} + \varepsilon_{ijklmn}$$

Where:

- β_0 : Intercept

Clinical Study Protocol

Johnson & Johnson Vision Care, Inc.

- $Lens_i$: $Lens_i=1$ if Lens='-1.00DC'; otherwise $Lens_i=0$
- $Period_j$: $Period_j=1$ if period=1; otherwise $Period_j=0$
- $Sequence_k$: $Sequence_k=1$ if sequence=-1.00/-1.75; otherwise $Sequence_k=0$
- δ_l : effect of the l^{th} site, a random effect
- γ_{l_m} : effect of the m^{th} subject from the l^{th} site, a random effect
- ε_{ijklm} : Random error associated between eyes (left and right) for the m^{th} subject from the l^{th} site assigned to the k^{th} sequence during the j^{th} period for the i^{th} lens

Assume δ_l , γ_{l_m} and ε_{ijklm} are independent and

- $\delta_k \sim N(0, \sigma_{site}^2)$
- $\gamma_{l_m} \sim N(0, \sigma_{subject(site)}^2)$

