- $$\begin{bmatrix} \varepsilon_{ijklm_Left} \\ \varepsilon_{ijklm_Right} \end{bmatrix} = \begin{pmatrix} [0] & \begin{bmatrix} \sigma_{11}^2 & \sigma_{12}^2 \\ \sigma_{21}^2 & \sigma_{22}^2 \end{bmatrix} \end{pmatrix}$$

Primary Hypothesis

The null and alternative hypothesis to test for superiority are as follows:

$$\begin{aligned} H_0: P_T &\leq 80\% \\ H_A: P_T &> 80\% \end{aligned}$$

Where P_T is the probability of the event (i.e., the probability of having absolute rotation less than 10° 15-minutes after insertion). Superiority will be concluded if the lower limit of the 95% confidence interval is above 80% (i.e., $P(p_{Test} > 80\%) \geq 0.975$).

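### When any fixed effect is significant, section 14.5 does not say which confidence limit decides superiority, and sections 2.3, 14.2 and 14.5 do not settle whether the pooled rate or each lens must exceed 80%

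*Combined protocol and SAP*

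**What the plan says.** Section 14.5 fits a logistic mixed model with sequence, period and lens as fixed effects, and allows covariates such as age. It then says: "If none of the fixed effects are significant, the percentage of lens fits with absolute rotation less than 10° will be estimated by combining" the two lenses' data, with two-sided 95% intervals. Nothing is said about the other case. The hypotheses that follow concern one probability, P_T, without a lens index, and the rule is "Superiority will be concluded if the lower limit of the 95% confidence interval is above 80"%. Section 2.3 likewise states that "the percentage of lens fits with absolute rotation less than or equal to 10 degrees will be superior to 80"%.

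Section 14.2 describes the target differently. It opens by powering the study to show that "the percentage of lens fit with absolute rotation for both study lenses is superior to 80"%, and it introduces Table 8 as giving the number of subjects needed to "test superiority for the primary hypothesis for each study lens". Its simulated success rule refers to one lower limit and does not say whose. The heading, "Table 8 Statistical Power for 80 Subjects to complete by Reference Rate", and the row label give power by reference rate only. On the simulation model: "Lens was included as the only fixed effect".

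Section 4.2 explains the small number of lens powers by saying that "rotation and lens power are expected to be independent". Section 14.4 sets a two-sided 5% level for the primary analyses; no level is given for the pooling condition. Section 14.6 lists no secondary analysis.

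**The concern.** This is the study's only confirmatory test, and a pretest on the trial data decides whether its result is a pooled percentage or something the plan does not define. If any effect is significant, at least two criteria are open: the pooled lower limit, or the lower limits of both lenses. They can disagree, and the choice would be made after the data are seen.

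The condition is also poorly matched to its purpose. A chance period or sequence effect stops the pooling, although neither bears on whether the lenses share a rate. A non-significant lens effect does not show that they do. It is unclear whether an added covariate such as age counts among the tests.

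A further gap is the scale of P_T. In a logit model with random subject effects, the percentage for a typical subject and the percentage of lens fits in the population are different quantities, and section 14.5 does not say which one is compared with 80%.

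**Working it through.** **1. Does Table 8 reveal its target?** Inputs from section 14.2: 80 completers, hence 160 fits per lens and 320 in all; threshold 80%; two-sided 5% (z = 1.96); reference rates 88, 89 and 90%; stated power 87.7, 95.1 and 98.3%.

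One lens, with 160 fits treated as independent: power = Φ[(p − 0.80)/√(p(1 − p)/160) − 1.96].

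- 88%: 0.08/0.02569 − 1.96 = 1.154, power 87.6%
- 89%: 0.09/0.02474 − 1.96 = 1.678, power 95.3%
- 90%: 0.10/0.02372 − 1.96 = 2.256, power 98.8%

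Both lenses pooled, simulated with the plan's correlations of 0.80 and 0.50 on the binary scale but analysed with independent errors (8,000 samples per rate): 86.9, 93.2 and 96.5%.

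Both sets lie within 2 points of Table 8, so the figures do not show whether one lens or the pooled rate was powered. Neither calculation is the analysis that section 14.2 describes.

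**2. If Table 8 is power for one lens, what is the power for both?** At 88% the lower bound is 2 × 0.877 − 1 = 75.4%, independence gives 0.877² = 76.9%, and the upper bound is 87.7%. The plan's correlations imply a correlation between lens means of 0.50/[(1 + 0.80)/2] = 0.556, which gives about 80%. The bounds are 90.2-95.1% at 89% and 96.6-98.3% at 90%. If Table 8 is already joint or pooled power, none of this applies.

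**3. How often does the pooling condition fail by chance?** Assume three independent tests at 5% each and no true effects: 1 − 0.95³ = 14.3%.

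**4. How often does the unwritten choice then matter?** Simulation with 40,000 replicates per rate: 80 subjects, 40 per sequence, two lenses by two eyes, identical lenses. Contrasts are cluster-robust on the logit scale at 5% each, and limits are clustered 95% limits. Each pair of figures takes the 0.80/0.50 correlations on the binary scale, then on the latent scale.

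| True rate | Condition fails | Fails, pooled limit passes, both lens limits do not |
|---|---|---|
| 88% | 13.4 / 14.2% | 4.4 / 6.3% of all trials |
| 89% | 13.9 / 14.3% | 4.7 / 6.4% |
| 90% | 13.9 / 14.9% | 4.2 / 5.6% |

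The reverse disagreement did not occur. A separate run with probability-scale contrasts (8,000 replicates per cell) gave 13.6-14.3% and 4.5-6.8%.

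**5. How far apart are the targets?** At 88%, the clustered intervals pass in 57-73% of trials for the pooled rate and in 29-35% for both lenses. Small approximate random-intercept model simulations (150-300 samples) gave 96-99% pooled, 78-93% for one lens and 66-87% for both. The levels depend on coding choices that the plan does not fix. In each approach the pooled target is easier to meet than the both-lenses target.

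**The case against.** The best defence is that section 14.2 already supplies a default. The lead-in to Table 8 refers to each lens, and the simulated limit belongs to a least-squares mean from a model containing only lens. Lens-specific limits could then be the rule and pooling the exception. This stands in part: section 14.2 is not silent, and it would be too strong to say that Table 8 has no stated target anywhere. But the text still does not say whether one lens or both must pass, why a period effect should trigger the change, or how this fits the single P_T of sections 2.3 and 14.5.

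Three stronger readings are tempting and are not supported.

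- *The pretest costs a large share of power.* That follows only if every trial failing the condition counts as unsuccessful, a rule the plan does not contain. In a 20,000-replicate run at 88%, overall passes are 56.3/72.1% (binary/latent) if the pooled limit decides such trials and 51.6/65.5% if both lens limits decide. The gap of 4.7/6.6 points is the effect of the ambiguity.
- *False positives are materially inflated.* With both lenses truly at 80%, the pooled limit passes in 2.1/2.3% of trials. Accepting any passing limit once the condition fails gives 2.7/3.3%, against a nominal 2.5%. This covers identical lenses only.
- *The planned model is known to distort the percentage by a given amount.* Subject-specific and population percentages do differ, but the check available was an intercept-only fit without the lens, period, sequence, site and between-eye terms of section 14.5. No size is claimed.

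It is also fair to say that section 4.2 explains the choice of powers and does not define an estimand. It gives no reason for a pretest, but it does not oblige the sponsor to choose pooling.

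**Conclusion.** The concern holds as a gap in the decision rule. The plan does not name the deciding limit when any fixed effect is significant, and its sections do not agree on the target. This rests on the text and is secure.

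The sizes are less secure. The 14% assumes three independent 5% tests and identical lenses. The 4-7% comes from a clustered-interval approximation, not the planned mixed model. A rough, unvalidated fit closer to section 14.5, with 2-21% non-convergence, failed the condition in 45-69% of trials. It is not relied on, but it shows that 14% should not be read as a property of the planned analysis.

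A reader might infer that Table 8 is wrong or that the study is underpowered. The documents do not support that: Table 8 can be matched under more than one target, and the lower pass rates above come from approximations. What can be said is that its power figures cannot be tied to one success criterion.

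**What to change.** Delete the significance-conditional clause in section 14.5 and pre-specify one unconditional criterion:

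- **(a)** the single P_T of section 2.3, averaged equally over the two lenses, with superiority if its lower 95% limit exceeds 80% and lens-specific intervals reported as supportive; or
- **(b)** if section 14.2's both-lenses claim is intended, superiority only if each lens's lower 95% limit exceeds 80%.

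Under either option, period and sequence stay in the model but do not select the estimand. State that P_T and its interval refer to the population percentage of lens fits on the probability scale, and how they are obtained from the model, for example by averaging predicted probabilities over the random-effect distribution. Align sections 2.3, 14.2 and 14.5, label Table 8 with the chosen target, rerun its simulation under the chosen rule, and restate the power if it differs.

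The cost is rewording and one simulation rerun, with no new data and no change to the sample size proposed here. The drawback is that the stated power may fall. If it drops below the plan's 80% target, the sponsor will have to decide how to respond.

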14.6. Secondary Analysis

Not applicable.

14.7. Other Exploratory Analyses

Exploratory endpoints will be descriptively summarized.

14.8. Interim Analysis

No interim analysis will be conducted on this study.

14.9. Procedure for Handling Missing Data and Drop-Outs

Missing or spurious values will not be imputed. The count of missing values will be included in the summary tables and listings.

14.10. Procedure for Reporting Deviations from Statistical Plan

The analysis will be conducted according to that specified in above sections. There are no known reasons for which it is planned to deviate from these analysis methods. If for any reason

Clinical Study Protocol

Johnson & Johnson Vision Care, Inc.

a change is made, the change will be documented in the study report along with a justification for the change.

15. DATA HANDLING AND RECORD KEEPING/ARCHIVING

15.1. Electronic Case Report Form/Data Collection

The data for this study will be captured on electronic case report forms (eCRFs) using an EDC system (Bioclinica). An authorized data originator will enter study data into the eCRFs using the EDC system. Data collected on equipment that is not captured in EDC will be formatted to the specification of the JJVC database manager and sent to JJVC for analysis.

The clinical data will be recorded on dedicated eCRFs specifically designed to match the study procedures for each visit. Only specifically delegated staff can enter data on a CRF. Once completed, the eCRFs will be reviewed for accuracy and completeness and signed by the Investigator. The sponsor or sponsor's representatives will be authorized to gain access to the subject recordation for the purposes of monitoring and auditing the study.

Edit checks, electronic queries, and audit trails are built into the system to ensure accurate and complete data collection. Data will be transmitted from the clinical site to a secure central database as forms are completed or updated, ensuring information accuracy, security, and confidentiality. After the final database lock, the Investigator will be provided with Individual Patient Profiles (IPP) including the full audit trail on electronic media in PDF format for all of the study data. The IPP must be retained in the study files as a certified copy of the source data for the study.

The content and structure of the eCRFs are compliant with ISO14155:2020.¹

15.2. Subject Record

At a minimum, subject record should be available for the following:

- subject identification
- eligibility
- study identification
- study discussion
- provision of and date of informed consent
- visit dates
- results of safety and efficacy parameters as required by the protocol
- a record of all adverse events
- follow-up of adverse events
- medical history and concomitant medication
- test article receipt/dispensing/return records
- date of study completion
- reason for early discontinuation of test article or withdrawal from the study, if applicable

Clinical Study Protocol

Johnson & Johnson Vision Care, Inc.

The subject record is the eCRF or an external record. The author of an entry in the subject record must be identifiable. The first point of entry is considered to be the source record.

Adverse event notes must be reviewed and initialed by the Investigator.

15.3. Trial Registration on ClinicalTrials.gov

This study will be registered on ClinicalTrials.gov based on the following: The purpose of the study is for design confirmation, not feasibility.

16. DATA MANAGEMENT

16.1. Access to Source Data/Document

The Investigator/Institution will permit trial-related monitoring, audits, IEC/IRB review and regulatory inspection(s) by providing direct access to source data/documents. Should the clinical site be contacted for an audit by an IEC/IRB or regulatory authority, JJVC must be contacted and notified in writing within 24 hours.

16.2. Confidentiality of Information

Information concerning the investigational product and patent application processes, scientific data or other pertinent information is confidential and remains the property of JJVC. The Investigator may use this information for the purposes of the study only. It is understood by the Investigator that JJVC will use information developed in this clinical study in connection with the development of the investigational product and therefore may disclose it as required to other clinical investigators and to regulatory agencies. In order to allow the use of the information derived from this clinical study, the Investigator understands that he/she has an obligation to provide complete test results and all data developed during this study to the Sponsor.

16.3. Data Quality Assurance

Steps will be taken to ensure the accuracy and reliability of data, include the selection of qualified investigators and appropriate clinical sites and review of protocol procedures with the Principal Investigator. The Principal Investigator, in turn, must ensure that all Sub-Investigators and clinical site personnel are familiar with the protocol and all study-specific procedures and have appropriate knowledge of the study article.

Training on case report form completion will be provided to clinical site personnel before the start of the study. The Sponsor will review case report forms for accuracy and completeness remotely during the conduct of the study, during monitoring visits, and after transmission to data management. Any data discrepancies will be resolved with the Investigator or designee, as appropriate.

Clinical Study Protocol

Johnson & Johnson Vision Care, Inc.

Quality Assurance representatives from JJVC may visit clinical sites to review data produced during the study and to assess compliance with applicable regulations pertaining to the conduct of clinical trials. The clinical sites will provide direct access to study-related source data/documents and reports for the purpose of monitoring and auditing by JJVC and for inspection by local and regulatory authorities.

